### **2.5.3 Allocation to treatment**

Patients will be assigned to their group based on a randomization scheme generated by a computer. Randomization is first stratified by location of the institution, then by random blocks within each institution. Once the assignment list is generated for each institution, the assignments are then placed in sealed, numbered, envelopes. The patients are assigned on a 1:1 basis between the two groups.

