## **2.3 Study design**

### **2.3.1 General study design**

This study is a randomized controlled trial. It is not blinded to either investigator or patient.

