## **2.5 Study procedures**

### **2.5.1 Screening procedures**

Patients are identified for the study by universal cervical length screening performed by ultrasound during the 2nd trimester. Once identified, patients are approached by study investigators who are authorized to obtain informed consent. The counseling will take place in the privacy of the ultrasound suite or a private clinic room. Both a medical history and physical exam are performed to verify if a patient meets criteria for enrollment in the study. The physical exam includes a sterile speculum exam which investigates for vaginal or cervical infections in symptomatic patients.

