## **4.0 DESCRIPTION OF THE INVESTIGATIONAL DEVICE**

Please see NAMSA report for description of cytotoxicity, sensitization, irritation, acute systemic toxicity, subchronic systemic toxicity, genotoxicity, implantation, chronic systemic toxicity in detail.

In this study, the Arabin pessary will be for single patient use only. Each enrolled patient will be given their own new pessary. The patient will use the same pessary throughout the length of the study.

Please see MEDCERT certificates for information regarding manufacturing, quality management, and distribution. Pessaries are stored at room temperature and do not require special packaging. The principal investigators “install” the pessaries after they are appropriately trained by a video tutorial.

The following description is *modified* from <http://www.dr-arabin.de/e/cerclage/html>

The Arabin pessary is a ring manufactured from medical grade silicone. It has outer and inner diameters that vary, a height when laid flat, and a curvature to one side of the pessary. The width of the outer and inner diameters are chosen depending on the individual constitution of the pregnancy patient. The curvature of the pessary is upwards so that the pelvic floor supports the larger diameter. The smaller, inner diameter encompasses the cervix. After application the pessary changes the inclination of the cervical canal, directing it more posteriorly (figure 1). Thus the weight of the pregnancy is more on the anterior lower segment, as can be observed by TVS in selected cases. The use of a spreading gliding compound facilitates pessary insertion. The silicone material is inert and does not react with the vaginal epithelium or cervical epithelium. The silicone pessary does not change during its placement in the vaginal canal. In general, singleton pregnancies require a pessary height of 21-25 mm, and multiple pregnancies require a pessary height of 25-30 mm.

There are 13 sizes of the Arabin cervical pessary, differing by their outer diameter, inner diameter, and height. The investigators will be appropriately trained according to instructional videos. If insufficient, there are provision plans to be trained in person by the manufacturer. The pessary size will be selected based on a best fit to the patient’s anatomy. This proper fit will help obviate the risk of cervical amputation.

[figure not shown]

Figure 1

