### 9.2 Record maintenance and retention

The sponsor-investigator will maintain records in accordance with 21 CFR 812, Subpart G, to include:

- FDA correspondence related to the IDE application and Investigational Plan; including copies of submitted Form FDA 3500A, supplemental IDE applications, current investigator lists, progress reports, notice of device recall or disposition, and failure to obtain informed consent reports
- IRB correspondence (including approval notifications) related to the clinical protocol; including copies of adverse event reports and annual or interim reports
- Current and past versions of the IRB-approved clinical protocol and corresponding IRB-approved consent form(s) and, if applicable, subject recruitment advertisements
- Signed Investigator's Agreements and Certifications of Financial Interests of Clinical Investigators
- Curriculum vitae (sponsor-investigator and clinical protocol sub-investigators)
- Certificates of required training (e.g., human subject protections, Good Clinical Practice, etc.) for sponsor-investigator and listed sub-investigators
- Normal value(s)/range(s) for medical/laboratory/technical procedures or tests included in the clinical protocol
- Laboratory certification information

- Instructions for on-site preparation and handling of the investigational device and/or study treatment or diagnostic product(s), and other study-related materials (i.e., if not addressed in the clinical protocol)
- Master randomization list
- Signed informed consent forms
- Completed Case Report Forms, signed and dated by sponsor-investigator
- Source Documents or certified copies of Source Documents
- Monitoring visit reports
- Copies of sponsor-investigator correspondence to sub-investigators, including notifications of adverse effect information
- Subject screening and enrollment logs
- Subject identification code list
- Investigational device accountability records, including documentation of device disposal
- Interim data analysis report(s)
- Final clinical study report.

The sponsor-investigator will retain the specified records and reports for up to two years after the marketing application is approved for the investigational device; or, if a marketing application is not submitted or approved for the investigational device, until two years after investigations under the IDE have been discontinued and the FDA so notified.

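### Allocation concealment (2.5.3, 9.2): pre-filled envelopes in open-label, site-stratified blocks, with no stated bar on access to the master list, do not prevent enrolling investigators from knowing or guessing some upcoming assignments

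*Combined protocol and SAP*

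**What the plan says.** All references are to the combined protocol and SAP.

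- **Blinding (2.3.1):** "It is not blinded to either investigator or patient".
- **Sequence (2.5.3):** "Patients will be assigned to their group based on a randomization scheme generated by a computer". The structure is: "Randomization is first stratified by location of the institution, then by random blocks within each institution". The ratio is 1:1 and no block size is given.
- **Concealment (2.5.3):** "Once the assignment list is generated for each institution, the assignments are then placed in sealed, numbered, envelopes".
- **Who enrols (2.5.1):** once screening ultrasound has identified a short cervix, "patients are approached by study investigators who are authorized to obtain informed consent". History and physical examination are used to confirm eligibility.
- **Records (9.2):** "The sponsor-investigator will maintain records in accordance with 21 CFR 812, Subpart G, to include", followed by a list in which one item is "Master randomization list".
- **Primary analysis (2.6.3):** a chi-square or Fisher's exact test of two proportions, with no baseline adjustment.

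The document does not say who generates the list or fills the envelopes, who holds them and where, whether they are opaque, whether they must be opened in order, or whether consent and eligibility must be on record before one is opened. It does not restrict access to the list while enrolment is open.

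**The concern.** With no blinding after allocation, concealment before allocation is what keeps the two arms comparable. Here the enrolling investigator knows the main prognostic facts beforehand: cervical length is the entry test, and history and examination precede enrolment.

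Some eligibility decisions also involve judgement. Section 2.4.4 would include women with a prior cone biopsy unless their anatomy rules out placing a pessary, a question that matters in practice for one arm only. If the next assignment is known or can be guessed, a woman may be deferred, excluded or counselled differently because of it, without any bad faith.

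Intention-to-treat analysis cannot repair selection that happens before randomisation, and an unadjusted test does not correct for the resulting imbalance. The success rule in 2.6.3 depends on statistical significance of that comparison, together with a limit on incomplete data.

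**Working it through.** **1. The plan's own figure.** Inputs from 2.6.2: 30% vs 15%, 80% power, two-sided 0.05, pooled z-test.

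n per arm = [1.960·√(2·0.225·0.775) + 0.842·√(0.30·0.70 + 0.15·0.85)]² / 0.15² = 120.5, so 121 per arm and 242 in total. This matches the plan. Allowing for 5% loss, 242/0.95 = 254.7, so 255 against the 256 stated. The sample size is not in dispute; 121 per arm is used below.

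**2. How predictable are blocked assignments?** Assume past assignments at a site are known (the trial is open-label) and the block size is fixed and known. No block size is stated, so a range is shown, from enumerating all permuted 1:1 blocks.

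| Block size | Assignments certain | Best guess correct |
|---|---|---|
| 2 | 50% | 75% |
| 4 | 33% | 71% |
| 6 | 25% | 68% |
| 8 | 20% | 67% |

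If sizes vary at random, always guessing the arm that is behind is right about 70% of the time (sizes 2/4/6) or 68% (sizes 4/6/8), by simulation. Varying sizes remove most of the certainty but not the better-than-chance guess.

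**3. Effect of steering when there is no true effect.** Assumptions, none from the documents: half the women have 45% preterm risk and half 15% (mean 30%). A share s of high-risk women is turned away when the next slot is thought to be pessary, and the same share of low-risk women when it is thought to be control.

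If every assignment is known:
- High-risk share in the pessary arm = 0.5(1−s)/[0.5(1−s)+0.5].
- s = 20%: 0.4/0.9 = 0.444, so the pessary rate is 0.444·0.45 + 0.556·0.15 = 28.3%. The control rate is 31.7% and the difference is 3.33 points.
- s = 30%: 0.35/0.85 = 0.412, giving 27.4% vs 32.6%, a difference of 5.29 points.

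The two-sided 5% test declares a benefit when the observed difference exceeds 1.960·√(2·0.3·0.7/121) = 0.1155. With a standard error of about 0.0589:
- s = 20%: Φ[(0.0333 − 0.1155)/0.0589] = Φ(−1.40) ≈ 8%.
- s = 30%: Φ[(0.0529 − 0.1155)/0.0588] = Φ(−1.06) ≈ 14%.

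If only some assignments are known, the difference is scaled down. Steering on certain assignments in blocks of 4 keeps one third of it. Best-guess steering keeps about 2·0.708 − 1 = 42%.

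| What the enroller knows | s = 20% | s = 30% |
|---|---|---|
| Nothing | 2.5% | 2.5% |
| Certain assignments, fixed blocks of 6 | 3.4% | 4.1% |
| Certain assignments, fixed blocks of 4 | 3.8% | 4.8% |
| Best guess, fixed blocks of 4 | 4.2% | 5.6% |
| Every assignment (worst case) | about 8% | about 14% |

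The entries are one-sided false-benefit rates. With milder risk classes (40%/20%), the worst case is 5.7% to 8.7% and best guess in blocks of 4 gives about 3.6% to 4.4%.

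**4. Direction.** Steering high-risk women towards the pessary instead reverses the sign. The same figures then apply to a false finding of harm, and a real benefit would be diluted.

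**The case against.** The strongest reply is that this is silence, not a defect. The envelopes are sealed and numbered, the list is computer-generated, and 2.5.3 speaks of random blocks, which may mean varying sizes. Much of this stands.

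- **A reader might infer that recruiters can see the next assignment.** No passage gives enrolling staff sight of the list.
- **A reader might infer that the envelopes are kept at each site.** Section 2.5.3 says a list is generated for each institution, not where the envelopes are stored.
- **A reader might take 9.2 as proof that the sponsor-investigator holds the list during accrual.** Section 9.2 is a retention list that also contains the final study report. It leaves custody during accrual open, neither showing access nor excluding it. Section 4.0, under which the principal investigators place "the pessaries after they are appropriately trained by a video tutorial", describes what happens after allocation and adds nothing on concealment.
- **A reader might take 8% to 14% as the expected error.** It needs every assignment to be known. Guessing within blocks, which the text does leave possible, gives about 4% to 6%.
- **A reader might assume the bias favours the pessary.** Section 3.1 records a belief that the device outperforms current therapy, and an enroller who shares it could as easily steer the shortest cervices towards the pessary.

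There are also partial safeguards: screening and enrolment logs (9.2), cervical length and gestational age recorded at randomisation (synopsis), and monthly chart audits (5.0). These could expose an imbalance afterwards. They do not prevent one, and the planned test does not adjust for it. Well-specified envelopes would also be acceptable, but 2.5.3 does not specify them well.

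**Conclusion.** The point holds as a weakness of the concealment method: the plan does not prevent foreknowledge or guessing of some assignments, by investigators who already know each woman's prognosis. The documents do not show that this occurred or that anyone had access to the list.

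The size is modest if only guessing is possible: a false-benefit rate of about 4% to 6% against 2.5% in fixed blocks of 4, and somewhat less if block sizes vary. It becomes serious, about 8% to 14%, only if the whole list is known. These figures rest on assumed risk classes, steering rates and block size, and the bias could run in either direction.

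The sponsor should make the change because it is cheap and removes an avoidable risk. It concerns the plan and not a reported result: the cover letter states that the trial closed with 7 women and that no tests were run.

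**What to change.** - **2.5.3:** replace the envelopes with one-at-a-time release through REDCap, already used for the case report forms (2.5.6, 9.1), after consent, confirmed eligibility and baseline cervical length have been saved. State that block sizes vary and are not disclosed to the sites.
- **Fallback if envelopes are kept:** opaque envelopes opened strictly in sequence, with subject ID, date and time written on each before it is opened.
- **9.2:** state that the list is generated and held by someone who does not screen, consent or fit pessaries, and that it passes to the sponsor-investigator's file only after the last woman is randomised.

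Cost: one paragraph in 2.5.3, one line in 9.2, a non-enrolling list holder, and a short login or logging step at each enrolment. No additional patients or visits are needed and the sample size is unchanged.

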### **2.5.4 Treatment adherence**

Patients are asked to return to clinic at frequent intervals for an evaluation that includes history, transvaginal ultrasounds, and physical exam if needed. The pessary patients will return every 2 weeks after the pessary is placed. The control patients will have a weekly transvaginal ultrasound up to 24 weeks, then a clinic visit every 2 weeks.

### **2.5.5 Withdrawal of subjects due to non-compliance**

An intent-to-treat analysis will be used for analyzing study results. In the pessary group, if a patient removes the pessary, their outcomes will still be analyzed in the pessary group. In the control group, if patients do not use vaginal progesterone, their results are still analyzed in the control group. Patients who receive emergency cerclages are 100% compliant.

If patients do not return for their clinic visits or their delivery information is lost, their data cannot be analyzed. The investigators will call a minimum of 2 times, separated by a week, to ensure follow up. If unsuccessful, a letter will be mailed to the address of record requesting follow up. With regards to the primary outcome of preterm delivery, they will be assumed as having delivered the pregnancy at the gestational age they were lost to follow up.

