#### 1.4.2 Secondary Objectives

- Neonatal composite morbidity – fetal or neonatal death, respiratory distress syndrome (RDS), chronic lung disease, periventricular lucency, periventricular leukomalacia, intraventricular hemorrhage grade 3 or 4, necrotizing enterocolitis, early-onset-culture-proven sepsis
- Neonatal length of stay
- Neonatal NICU admission
- Total NICU days
- Duration of ventilator support
- retinopathy of prematurity (ROP) requiring treatment
- birthweight < 1500g and < 2500g
- preterm birth < 34 weeks
- gestational age at delivery
- use of tocolysis
- use of antenatal steroids
- chorioamnionitis
- vaginal bleeding
- preterm premature rupture of membranes
- cesarean delivery

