### **2.6.3 Outcome data and data analysis**

When patients are admitted to the hospital for delivery of the fetus, the research team will record the information listed on the REDCap CRF. Both the mother and newborn hospital charts will be reviewed for the primary and secondary outcomes listed in sections 1.4.1 and 1.4.2. If patients deliver at another hospital, those records will be obtained with the patient's consent.

De-identified data from each institution will be stored on the REDCap website. That data will be downloaded into either Excel or SAS format for analysis. This file will be stored in the folder of [name] MD, on the network server named "Sydney". This drive is password protected. Only members of the research team will be given access to the stored data.

The primary endpoint and the categorical outcomes that are part of the secondary endpoints will be reported using frequency counts and proportions. For the secondary endpoints that are continuous variables, summary statistics such as mean and standard deviation, or median and inter-quartile range will be reported based on whether the assumption of normality is justified. A chi-square test (or a Fisher's exact test) will be used to perform statistical comparison of proportions across the two groups. Likewise, comparisons for continuous outcomes will be done using a two-sample t-test (or Wilcoxon Rank Sum test) as will be deemed necessary. For gestational age, we will also compare the Kaplan Meier survival curves of the two groups (control and pessary) using the logrank test. Level of significance for all statistical tests will be set at 0.05.

As mentioned before, subjects lost to follow up will have the gestational age at delivery set at the point data was lost. An intent to treat analysis will then be performed. A sensitivity analysis will be conducted by omitting the incomplete data and recalculating the differences between the pessary and control groups. The changes in results will then be compared.

The Arabin pessary will be considered a success if the following conditions are met: 1) a statistically significant reduction of preterm birth is found in the group treated with the Arabin pessary, 2) the number of patients with incomplete data does not exceed 10%. If a statistically significant difference is observed, but missing data is equal or greater than 10%, then additional study with a larger sample size is warranted.

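### Once calls and a letter fail, no readable section requires asking the obstetrician whether the unapproved pessary is out or when the woman delivered

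*Combined protocol and SAP*

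**What the plan says.** Section 2.5.5 sets the procedure for a woman who no longer attends. It begins: "The investigators will call a minimum of 2 times, separated by a week, to ensure follow up". It continues: "If unsuccessful, a letter will be mailed to the address of record requesting follow up". Both steps are directed at the woman herself. If they fail, then for the primary outcome "they will be assumed as having delivered the pregnancy at the gestational age they were lost to follow up". Section 2.6.3 repeats the rule: "subjects lost to follow up will have the gestational age at delivery set at the point data was lost". The rule therefore also reaches "gestational age at delivery", a secondary endpoint in section 1.4.2, and its Kaplan-Meier comparison.

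Other provisions bear on the point:

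- Section 2.6.3 gives routes to delivery data. On admission for delivery, "Both the mother and newborn hospital charts will be reviewed for the primary and secondary outcomes". For deliveries elsewhere: "If patients deliver at another hospital, those records will be obtained with the patient's consent".
- Section 2.6.3 plans a check on the rule: "A sensitivity analysis will be conducted by omitting the incomplete data". It also makes success conditional on no more than 10% of patients having incomplete data.
- Section 2.5.2 states that the device lacks FDA approval and schedules removal at 37 weeks, or earlier for labor, erosion or intractable pain. It sends a copy of each clinic note to the primary obstetrician. That is the only communication with the obstetrician in the readable text, and it runs one way.
- Section 3.1 lists cervical amputation and tissue erosion among the risks, and relies on two-weekly evaluation to limit harm.
- Section 5.0 has monthly chart audits for data accuracy. Section 9.2 requires device accountability and disposal records. Neither sets a tracing step.

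**The concern.** When a pessary wearer stops attending, the two-weekly checks that protect her stop too. Calls and a letter may bring her back. If they do not, the written procedure ends, and no required step establishes whether the device is still in place. Another clinician who is likely to know, and who already receives the study's notes, does not have to be asked. Harm from a retained device could go unseen.

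The same unasked question affects the primary endpoint. A woman lost at, say, 28 weeks who delivers at term counts as a preterm birth, although one inquiry might have supplied the true date. With equal loss unrelated to outcome, this shrinks the difference between the arms. With unequal loss it can move the difference either way.

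**Working it through.** **Inputs.** Section 2.6.2: 30% against 15% preterm birth, two-sided pooled z-test, alpha 0.05, power 80%, 242 for analysis, 5% loss, 256 enrolled. Section 2.5.3: 1:1 allocation, so 128 per arm.

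**Reproducing the plan.** With p̄ = 0.225, n per arm = [1.96·√(2 × 0.225 × 0.775) + 0.842·√(0.30 × 0.70 + 0.15 × 0.85)]² / 0.15² = 120.5, so 121 per arm and 242 in total, as stated. Then 242/0.95 = 254.7, so 255, or 256 for equal arms.

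**Women lost.** Pessary arm: 128 × 0.05 = 6.4; the 2.5th and 97.5th percentiles of binomial(128, 0.05) are 2 and 12. Both arms: 256 × 0.05 = 12.8, range 6 to 20.

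**Effect of the scoring rule.** Assume every untraced loss occurs before 37 weeks and is unrelated to outcome. With L the untraced fraction, the scored rate is p(1 − L) + L. At L = 0.05:

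- control: 0.30 × 0.95 + 0.05 = 0.335
- pessary: 0.15 × 0.95 + 0.05 = 0.1925

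Power = Φ{[(p₁ − p₂) − 1.96·√(2p̄(1 − p̄)/n)] / √([p₁(1 − p₁) + p₂(1 − p₂)]/n)}. With n = 128 and p̄ = 0.26375, this is Φ[(0.1425 − 1.96 × 0.05508)/0.05436] = Φ(0.635) = 73.7%.

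| Equal 5% loss | Rates compared | Power |
|---|---|---|
| None traced | 33.5% vs 19.25% | 73.7% |
| Half traced | 31.75% vs 17.125% | 78.1% |
| All traced | 30% vs 15% | 82.4% |
| Lost women omitted (121.6 per arm) | 30% vs 15% | 80.4% |

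Before rounding, the gap between none and all traced is 8.6 points. Of these, 6.6 separate the scoring rule from simple omission, and 2.0 reflect fewer women analysed.

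**Unequal loss.** The documents give no split by arm; 7.5% and 2.5% is an assumption.

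| Loss, pessary / control | Difference as scored | Power as scored | Power, lost women omitted |
|---|---|---|---|
| 7.5% / 2.5% | 10.4 points | 46.8% | 80.2% |
| 2.5% / 7.5% | 18.1 points | 91.4% | 80.4% |

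With no true effect (30% in both arms) and 2.5% / 7.5% loss, the scored rates are 31.75% pessary and 35.25% control. The chance of a significant result favouring the pessary is then 8.6% as scored and 2.5% with lost women omitted.

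**Contacts needed.** 12.8 women × 2 occasions = 25.6, about 26, if only the obstetrician is contacted. With the hospital as well, 12.8 × 4 = 51.2, about 51.

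**The case against.** The strongest reply is that the primary-outcome figures mostly measure something else. The scoring rule, not the missing contact, produces 6.6 of the 8.6 points, and the largest distortions also need an assumed imbalance in loss. If loss is unrelated to outcome, the planned analysis without incomplete data restores about 80% power and a 2.5% chance of false benefit, even with unequal loss. The 10% limit is a second guard. This stands. But that analysis is a sensitivity analysis and does not replace the primary test, the 10% limit would not act at 5% loss, and neither concerns the device.

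A reader might infer that nothing beyond the calls and letter could find these women. The documents do not support that. Chart review at delivery does not depend on clinic attendance, outside records can be obtained with consent, and the two calls are a floor. These routes will recover some delivery dates. They are not written as steps for an unreachable woman, however, and records obtained at or after delivery do nothing timely about a device in place.

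On the device, labor triggers removal, section 2.5.5 anticipates self-removal, and section 3.1 calls the erosion concern extremely low. These considerations lower the likely number of retained devices but do not establish what happened to any one woman.

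Finally, the consent form and the case report forms (attachments under section 9.1) are not in the readable text and may cover record release or device removal. The point is limited accordingly.

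**Conclusion.** The point holds in a limited form, mainly on device safety. Followed exactly, section 2.5.5 can end with an unapproved device unaccounted for while a clinician who already receives the study's notes has not been asked. About 6 pessary women (2 to 12) would be expected lost at 5%. A reader might take that as a count of retained devices or a ceiling on them; it is neither. It is an expected number of lost women, and the 5% comes from past short-cervix patients, not pessary wearers.

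Secondarily, tracing would reduce the number of imputed deliveries. The range from 73.7% to 82.4% power is a worst case against an upper limit. It assumes that all 5% are untraced, lost before 37 weeks and unrelated to outcome; the plan does not say whether its 5% means missed visits or unknown deliveries. A reader might also infer that the missing contact by itself costs 8.6 points, or that a false-benefit chance of 8.6% is expected. The first belongs mostly to the scoring rule, and the second rests on a loss split with no source in the documents.

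The change should be made. Confidence is medium because the consent form and case report forms could not be read. The cover statement says the trial closed with 7 subjects and no tests, so this concerns the plan, not a result.

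**What to change.** In section 2.5.5, after the failed calls and letter, add contact with the primary obstetrician and, where known, the delivering hospital. Use the same steps and timing in both arms: once promptly, and once after the due date to obtain the delivery date. Apply the assumed-delivery rule only if this fails, and keep the planned sensitivity analysis.

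For pessary women, use the prompt contact to record whether and when the device was removed. If it cannot be accounted for, notify the medical monitor then, without waiting for the six-monthly review. Check first what the consent form and case report forms already allow, and add only what is missing.

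The cost is a protocol wording change with prior IRB approval (section 8.0), possibly consent wording, one new type of notice to the medical monitor, and about 26 to 51 contacts at 5% loss. Some women will remain untraced.

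### The primary analysis counts a woman lost before 37 weeks as a preterm birth, but the sample size assumes that losses leave the analysis, so the stated 80% power does not describe the planned test.

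*Combined protocol and SAP*

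**What the plan says.** Section 2.5.5 provides for at least two calls a week apart and then a letter. If these fail, the rule for the primary outcome is that "they will be assumed as having delivered the pregnancy at the gestational age they were lost to follow up". Section 2.6.3 has the same rule without limiting it to the primary outcome: "subjects lost to follow up will have the gestational age at delivery set at the point data was lost". The intent-to-treat analysis follows.

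Just before its rule, section 2.5.5 also says: "If patients do not return for their clinic visits or their delivery information is lost, their data cannot be analyzed".

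Section 2.6.2 and the synopsis require 242 women for analysis (30% versus 15%, 80% power, two-sided 0.05, pooled z-test) and enrol 256 to allow for 5% loss. In that calculation a lost woman contributes nothing.

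Section 2.6.3 contains several safeguards:
- On deliveries elsewhere: "If patients deliver at another hospital, those records will be obtained", subject to the patient's consent.
- A complete-case check: "A sensitivity analysis will be conducted by omitting the incomplete data and recalculating the differences between the pessary and control groups". It adds: "The changes in results will then be compared".
- A success rule that requires a significant reduction and that "the number of patients with incomplete data does not exceed 10" per cent.

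The same section plans a time-to-event comparison: "For gestational age, we will also compare the Kaplan Meier survival curves of the two groups (control and pessary) using the logrank test".

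**The concern.** A woman whose last contact is before 37w0d is known only to have been pregnant at that time. The rule turns this into a preterm birth. Because section 2.6.3 assigns her a gestational age at delivery, she also enters the log-rank comparison as a delivery at last contact, although that method could simply censor her.

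Two things are at stake. First, the sizing and the primary analysis treat the same women differently, so the stated power belongs to another analysis. If loss is equal and unrelated to outcome, the rule adds more false events to the arm with fewer true ones, which shrinks the difference. Second, if the arms lose women at different rates, the rule favours the arm that keeps more of them. The trial is open-label (section 2.3.1), so unequal loss is possible.

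**Working it through.** **Inputs from the plan.** Rates 30% and 15%, two-sided alpha 0.05, pooled z-test, 242 for analysis, 256 enrolled and 5% loss (section 2.6.2); 1:1 allocation, so 128 per arm (section 2.5.3). Timing of loss, true outcome of lost women and loss by arm are not given. They are varied below as assumptions.

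**The plan's own figure.** With p̄ = 0.225, n per arm = [1.96·√(2·0.225·0.775) + 0.8416·√(0.30·0.70 + 0.15·0.85)]² / 0.15² = [1.96·0.5906 + 0.8416·0.5809]² / 0.0225 = 120.5. This rounds up to 121 per arm, or 242. Then 242/0.95 = 254.7, so 256 is adequate. Power is 80.2% at 121 per arm and 80.4% at 256 × 0.95 / 2 = 121.6 per arm. The plan's arithmetic is correct if losses are removed.

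**Power under the written rule.** All 128 per arm are analysed. Power = Φ{[(p1 − p2)·√n − 1.96·√(2p̄(1 − p̄))] / √(p1(1 − p1) + p2(1 − p2))}.

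Let L = 0.05 in each arm and let f be the share of losses before 37w0d. Hold the overall true rates at 30% and 15%. Early-lost women have their arm's true rate, and women lost at or after 37w0d are term. The scored rate is then p′ = p + L·f·(1 − p).

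| Share lost before 37w0d | Control | Pessary | Power |
|---|---|---|---|
| All | 33.50% | 19.25% | 73.7% |
| Three quarters | 32.63% | 18.19% | 75.9% |
| Half | 31.75% | 17.13% | 78.1% |
| A quarter | 30.88% | 16.06% | 80.2% |

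For the first row: 0.30 + 0.05·0.70 = 0.335 and 0.15 + 0.05·0.85 = 0.1925. The power is Φ[(0.1425·√128 − 1.96·0.6232)/0.6150] = Φ(0.635) = 73.7%. Exact binomial enumeration gives 74.3%.

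Now let all losses be early, with a share q of the lost women in each arm truly delivering preterm, so p′ = p + L(1 − q):
- q = 0.5: 32.5% versus 17.5%, power 79.5%.
- q = 1: 30% versus 15%, power 82.4%, the same as 128 per arm with no loss.

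**Can losses fall after 37 weeks?** Yes. The last listed visit in section 2.5.8 is Day 112, or 16 weeks. That is 36w0d for the assumed enrolment at 20w0d and 37w0d for enrolment at 21w0d. The value of f cannot be read from the documents.

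**Type I error.** With no true effect (30% in both arms) and equal 5% early loss, both scored rates are 33.5%, and exact two-sided rejection is 5.05%.

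**Unequal loss, illustration only.** There is no true effect, loss averages 5%, and the scored rate is 0.30 + L·f·0.70. The last column is exact rejection in the pessary's favour (nominal 2.5%).

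| Control / pessary loss | Share early | Scored rates | False pessary benefit |
|---|---|---|---|
| 6% / 4% | Half | 32.1% / 31.4% | 3.3% |
| 6% / 4% | All | 34.2% / 32.8% | 4.3% |
| 8% / 2% | Half | 32.8% / 30.7% | 5.6% |
| 8% / 2% | All | 35.6% / 31.4% | 10.7% |

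Reversing the splits gives the same rates in the control's favour. Since 10% of 256 is 25.6, the limit allows 25 women with incomplete data. With binomial losses, both splits stay within it in over 99.9% of trials.

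**The case against.** The strongest reply is that the effect is modest and the plan already looks for it. The 74% needs every loss to be early, unrelated to outcome and without a retrievable delivery date. The 5% comes from routine records, and the calls, letter and record retrieval may lower it: at 2% loss, all early, power is 78.9%. If lost women truly deliver preterm more often than others, the cost shrinks or disappears. This stands, and it is why the result is a range that reaches above 80%.

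The complete-case analysis also keeps about the planned power and would reveal a discrepancy. That stands in part. But success in section 2.6.3 rests on the primary result and on total missingness. Agreement with the complete-case result is not required, and the limit is not by arm. In simulated trials with a true halving and equal 5% loss, all early, the two analyses disagreed on significance about 11% of the time.

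A reader might infer that section 2.5.5 contradicts itself outright, because it says lost women's data cannot be analysed and then says how to analyse them. The text does not force this. The later sentence is limited to the primary outcome and can be read as an exception. The wording is loose and needs clarifying.

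A reader might also infer that the rule is safely conservative, or that it favours the pessary. Neither follows. With equal loss unrelated to outcome it dilutes a benefit. With unequal loss the direction depends on which arm loses more, and the documents do not say.

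**Conclusion.** The mismatch is real and should be fixed. The primary analysis scores women last known pregnant before 37w0d as preterm births, while the 80% power was computed as if they were dropped. At 5% loss, equal by arm, power under the written rule is about 74% to 82%. The low end assumes that all losses are early and independent of outcome. The high end assumes that all lost women truly deliver preterm. It would be too strong to say that the trial's power is 74% or is certainly below 80%, because the documents give neither the timing nor the outcome of losses.

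Type I error stays nominal under equal loss. Bias from unequal loss is a possibility in either direction, and the splits shown are assumed. The cover statement reports 7 women enrolled and no tests run, so the point concerns the plan as written and touches no reported result.

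**What to change.** 1. In section 2.5.5, make clear that the sentence on data that cannot be analysed does not override the primary-outcome rule in section 2.6.3. State that a woman whose delivery date is retrieved is analysed with that date, even if she missed visits.
2. When the delivery date is unknown, do not score a delivery. Censor at last contact in the Kaplan-Meier and log-rank comparison. For the primary outcome, use the Kaplan-Meier probability of delivery before 37w0d, or imputation conditional on being pregnant at last contact. Count a woman last seen undelivered at or after 37w0d as not preterm. Keep the present rule and the complete-case analysis as sensitivity analyses. The choice of primary estimator is open to debate; using retrieved dates and censoring in the log-rank test is less so.
3. Report missingness by arm and add a simple tipping-point analysis, since censoring also assumes that loss is unrelated to outcome.
4. If the present rule stays primary, restate power in section 2.6.2 as about 74% to 82% at 5% loss, depending on the timing and true outcome of losses, or state that the 80% refers to the complete-case set.

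The cost is revised wording in sections 2.5.5, 2.6.2 and 2.6.3 and a little more analysis work, or a slightly less favourable stated power. No more patients and no new data collection are needed. A new primary estimator would also need its test named.
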